#### 9.4 Exploratory endpoint analysis

Exploratory endpoints will be analyzed to provide information on additional outcome measures and how the system and subject characteristics affect the outcome of the investigative treatment on post-amputation pain. For all endpoints, data will be collected as described in the Schedule of Procedures (Appendix A).

- Treatment effect in Group #2  
Group #2 will receive stimulation during the second half of the home trial (Weeks 5-8), and the proportion of successes and/or mean improvements in outcome measures during this phase will be compared to those during the sham stimulation phase. In addition, a repeated measures analysis may be conducted to determine the within-subjects improvement from sham to stimulation.

Global impression of change (Patient Global Impression of Change (PGIC))

Analyses of changes in average RLP

[REDACTED]

Analyses of changes in average PLP [REDACTED]

Analyses of changes in worst RLP [REDACTED]

Analyses of changes in worst PLP [REDACTED]

[REDACTED]

- Non-opioid medication usage

[REDACTED]

- Pain Catastrophizing Scale (PCS)

[REDACTED]

- Clinician Satisfaction Survey

[REDACTED]

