| 
Study Plan
                    | 
Amputees must have an average pain [REDACTED] to qualify
         Individuals with one or more lower extremity amputations reporting [REDACTED] pain [REDACTED] on the Brief Pain Inventory Short Form (BPI-SF [REDACTED]) will be considered for enrollment into the study. After informed consent is obtained, potential subjects will be evaluated for general eligibility. The individuals who satisfy the preliminary criteria will be asked to complete a [REDACTED] baseline diary to record their [REDACTED] post-amputation pain [REDACTED] for each amputated limb. Individuals must report [REDACTED] to qualify.
 
Percutaneous leads will be placed in the upper leg adjacent to the femoral and/or sciatic nerves
         Qualifying subjects will be randomized to either Group #1 (Treatment) or Group #2 (Control). In all subjects, leads will be placed percutaneously [REDACTED] [REDACTED] All subjects will be instructed to use the SPRINT Stimulator(s) continuously each day [REDACTED] during the [REDACTED] home trial. Initially, subjects will use the stimulation system [REDACTED]: in Group #1, the system will deliver electrical stimulation [REDACTED], while in Group #2, the system will deliver sham (placebo) stimulation. [REDACTED], Group #2 will begin receiving the investigative treatment
 |

[figure not shown]

Following the initial [REDACTED] home trial, subjects will continue using the stimulation system [REDACTED]. While Group #1 will continue receiving actual stimulation, Group #2 will begin receiving actual stimulation [REDACTED]. At the end of the home trial, subjects will return to the clinic to have their lead(s) removed. After lead removal, the subjects will be followed for 12 months.

**Daily medications affecting pain will be permitted at levels established during baseline and PRN (pro re nata) medications will be permitted as needed**

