In a series of case studies, peripheral nerve stimulation [REDACTED] eliminate pain in a majority of patients, but the traditional method of surgically placing the lead is time consuming and complex, which greatly limits its use. Thus, the major limitation of existing methods of peripheral nerve stimulation (PNS) is the need for a simple method of placing electrode leads [REDACTED].

*Our previous feasibility study suggests a simple percutaneous method of placing leads can reduce pain [REDACTED]*

We propose to address the limitations of existing methods with a percutaneous method [REDACTED]

[REDACTED]

[REDACTED]

***The present study will determine if our approach of percutaneously stimulating the nerves [REDACTED] will produce greater pain relief than the placebo effect***

The Sponsor, SPR Therapeutics, proposes to gather data on the safety and clinical effectiveness of electrically stimulating peripheral nerves to reduce post-amputation pain. This evaluation is a randomized, double-blinded, placebo-controlled, multicenter pilot study of the SPRINT Peripheral Nerve Stimulation (PNS) System for the treatment of post-amputation pain. The device consists of a [REDACTED] lead that delivers electrical stimulation [REDACTED]

[REDACTED]

In all subjects, leads will be placed percutaneously [REDACTED]

Initially, subjects will use the stimulation system [REDACTED] in Group #1, the system will deliver electrical stimulation [REDACTED], while in Group #2, the system will deliver sham (placebo) stimulation. This study will determine if the specific effect of the investigative treatment is [REDACTED] different than the placebo (sham) effect.

Following the [REDACTED] home trial, subjects will continue using the stimulation system [REDACTED]. While Group #1 will continue receiving actual stimulation, Group #2 will begin receiving actual stimulation as well [REDACTED].

All subjects will be instructed to use the SPRINT Stimulator(s) [REDACTED]. At the end of the home trial, subjects will return to the clinic to have their lead(s) removed. After lead removal, the subjects will be followed [REDACTED].

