#### 4.5 Exploratory Analyses

Additional analysis will be conducted including:

- Treatment effect in Group #2 [REDACTED]
- Global impression of change (Patient Global Impression of Change (PGIC)) [REDACTED]
- Analyses of changes in average RLP [REDACTED]
- Analyses of changes in average PLP [REDACTED]
- Analyses of changes in worst RLP [REDACTED]
- Analyses of changes in worst PLP [REDACTED]
- Non-opioid medication use [REDACTED]
- Pain Catastrophizing Scale (PCS) [REDACTED]
- Clinician Satisfaction Survey

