**9.1 Primary clinical efficacy endpoint analysis**

[REDACTED]

The effectiveness of percutaneous Peripheral Nerve Stimulation (PNS) for the treatment of post-amputation pain will be assessed in the present study. The goal of the proposed [REDACTED] study is to determine if the investigational treatment produces pain relief that is clinically meaningful and greater than the placebo effect. To distinguish between the effect of the investigational treatment and the placebo effect, qualifying individuals will be randomized (1:1) to either Group #1 (Treatment) or Group #2 (Control). The groups will be identical except for whether active stimulation (Group #1) or sham stimulation (Group #2) is delivered during the first 4 weeks of the home trial. Both groups are expected to experience a similar placebo effect from the study procedures and use of the devices. In Group #1, subjects will experience both the placebo effect and the investigational treatment effect. During the sham stimulation phase in Group #2, subjects will experience only the placebo effect. Thus, if there is a difference between the mean improvements during sham stimulation and active stimulation, it can be attributed to the investigational treatment effects.

The null hypothesis ( $H_0$ ) is that the investigational treatment (Group #1, active simulation) is equal to the control (Group #2, sham stimulation) in providing pain relief. The alternative hypothesis ( $H_1$ ) is that Group #1 has a proportion of successes that is not equal to the proportion of successes of Group #2.

1.  $H_0$ : proportion of successes of Group #1 = proportion of successes of Group #2
2.  $H_1$ : proportion of successes of Group #1  $\neq$  proportion of successes of Group #2

If the proportion of successes of the investigational treatment is statistically significantly greater ( $p < 0.05$ ) than the proportion of successes of the control during the first 4 weeks of the home trial and the alternative hypothesis is accepted at the 0.05 level of significance, it will indicate that the investigational treatment is clinically significant and different than the placebo effect.

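### Section 9.4 calls Group #2's change from sham to stimulation a treatment effect, but within that group stimulation cannot be separated from time since lead placement

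*Combined protocol and SAP*

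**What the plan says.** Section 4.5 lists "Treatment effect in Group #2" among the exploratory analyses, and Section 9.4 defines it. Group #2 receives stimulation in weeks 5-8 of the home trial, and "the proportion of successes and/or mean improvements in outcome measures during this phase will be compared to those during the sham stimulation phase". Section 9.4 then adds that "a repeated measures analysis may be conducted to determine the within-subjects improvement from sham to stimulation". It names no model, hypothesis, test or significance level for this item, and gives Group #1 no part in it.

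The order of treatment is fixed. Section 3.1 says of the later weeks: "While Group #1 will continue receiving actual stimulation, Group #2 will begin receiving actual stimulation as well". Group #1 is therefore on one condition throughout. Section 9.3 already uses Group #1's pain diaries over all 8 weeks for the first durability endpoint.

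Section 9.1 attributes an effect to the device in another way. The groups are to differ only in "whether active stimulation (Group #1) or sham stimulation (Group #2) is delivered during the first 4 weeks of the home trial", and "Both groups are expected to experience a similar placebo effect from the study procedures and use of the devices". There, the placebo response is removed by comparing the randomised groups.

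**The concern.** The reasoning of Section 9.1 does not carry over to Section 9.4. The Group #2 comparison has no concurrent control, so whatever else changes between weeks 1-4 and weeks 5-8 is counted together with stimulation. The documents suggest several candidates:

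- a placebo response that is still building or fading;
- continued weekly clinic contact;
- changes in as-needed medication, including increases in existing opioids as prescribed (Section 7.3);
- the visible imputation rule in Section 9.1.5, which replaces missing diary days with the baseline mean in the first 4 weeks only and so pulls the sham-phase mean toward no improvement.

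The bias can go either way: continuing improvement inflates the contrast, and a fading placebo response hides a real effect. What is at stake is the label. A quantity headed as a treatment effect invites a causal reading that Group #2's data alone cannot support.

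**Working it through.** **Inputs.** There are 27 subjects per group (Section 6.2). The plan gives no figure for this item to reproduce. Its expected success rates are redacted, and no SD, within-subject correlation or drift is visible. Assumed for scale: SD of a 4-week diary mean 2 points in each period, correlation ρ = 0.5 to 0.85, no device effect, and the same drift d in both groups.

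**1. What the contrast estimates.** Let S = 1 under stimulation and P = 1 in weeks 5-8. In Group #2, S = P for every subject. Hence

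E[weeks 5-8 minus weeks 1-4] = stimulation effect + period change.

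The two terms share one indicator, so no model fitted to Group #2 alone can separate them. A within-subject model removes differences between subjects but not this overlap. This step uses no assumed figure.

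**2. Scale for mean scores, if a paired t-test at two-sided 0.05 were used.** The SD of the change is 2√(2(1−ρ)): 2.00 at ρ = 0.5 and 1.10 at ρ = 0.85. The non-centrality is d√27 / SD of change, on 26 degrees of freedom.

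| Drift (points) | Non-centrality, ρ = 0.5 / 0.85 | False significance, ρ = 0.5 / 0.85 |
|---|---|---|
| 0.25 | 0.65 / 1.19 | 10% / 21% |
| 0.5 | 1.30 / 2.37 | 24% / 63% |

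Subtracting Group #1's change returns the rate to about 5%. That follows by construction, because the drift was set equal in the two groups.

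**3. Scale for success proportions.** Assume a shared rise from 15% to 25% with a latent normal correlation of 0.7 / 0.85. The chance of moving from failure to success is 0.145 / 0.123, and of moving back 0.045 / 0.023. Expected discordant pairs are 27 × 0.190 = 5.1, or 27 × 0.146 = 3.9. Exact McNemar at two-sided 0.05 is falsely significant for improvement in 7.6% / 6.6% of trials, against a nominal 2.5% in that direction. For a rise from 15% to 20% the figures are 1.8% / 1.1%.

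**4. What the difference of changes does.** Take a true effect of 0.5 SD and a shared drift of 0.3 SD. The one-arm contrast averages 0.5 + 0.3 = 0.8 SD.

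- Group #1's response stable: Group #2 minus Group #1 is 0.8 − 0.3 = 0.5 SD, which is correct.
- Group #1 still gaining 0.2 SD from stimulation: 0.8 − 0.5 = 0.3 SD, too small.
- Group #1's response fading by 0.2 SD: 0.8 − 0.1 = 0.7 SD, too large.

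**5. Precision.** At ρ = 0.5 the one-arm standard error is 2/√27 = 0.385 and that of the difference of changes is 2√(2/27) = 0.544. For a true 1-point effect the non-centralities are 2.60 and 1.84, giving power of about 71% and about 43-44%.

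**6. Why proportions need separate handling.** A doubling of the odds takes 15% (odds 0.176) to 26% (odds 0.353), a gain of 11 points. It takes 50% to 67%, a gain of 17 points. If the groups start from different rates, equal change on one scale is unequal change on the other, so the group-by-period term depends on the scale chosen.

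**The case against.** The best defence is that Section 9.4 promises only a comparison. Several Section 9.3 endpoints state hypotheses and a 0.05 level; this item states neither. It is one exploratory line in a pilot study, and attribution to the device rests on the randomised first 4 weeks. All of that stands. It means that the rates above show sensitivity under an assumed test and do not describe an error rate of the plan. It does not justify the label.

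Stronger readings are tempting and are not supported:

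- A reader might infer that the trial's main conclusion is affected. It is not: the primary comparison is between randomised groups.
- A reader might count regression to the mean from a high-pain baseline as a main source of bias. Both phases follow that baseline, so most of it cancels between them; only a slowly decaying part would remain.
- A reader might put the false-positive rate for success proportions at 21-26%. That needs the asymptotic McNemar test with only 4 to 5 discordant pairs, where it is unreliable.
- A reader might want the difference of changes to replace the planned contrast as the treatment effect, described as conservative. It is conservative only while Group #1 is still gaining, and it retains events specific to Group #2 at the switch, such as lead replacement at Visit 7 (Section 7.5).

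Text is also redacted directly after this item in Section 4.5 and at the end of Section 9.0, so a caveat may exist there. The paragraph in Section 9.4 appears complete and has none.

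**Conclusion.** The concern holds as a matter of labelling and reporting. In Group #2, stimulation and time since lead placement coincide exactly, and neither planned comparison separates them. This conclusion is structural and rests on no redacted figure.

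Its size cannot be known from the documents. Under the stated assumptions, a drift of a quarter to half a point could make a paired test misleading in roughly one trial in ten to six in ten. The exact responder comparison is much less sensitive. The remedy is worth making because the concurrent Group #1 data are already collected. The difference of changes is supportive evidence that needs its own assumption, so it should not stand as the sole estimate of treatment effect.

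**What to change.** In Section 9.4:

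1. Report Group #2's change from sham to stimulation as descriptive, and do not call it a treatment effect on its own.
2. Show Group #1's change from weeks 1-4 to weeks 5-8 beside it.
3. For mean pain scores, add Group #2's change minus Group #1's change (the group-by-period term in a repeated-measures model) with its confidence interval, as a supportive estimate.
4. State its assumptions: Group #1's response to stimulation is stable across the two periods (if it is growing, the estimate is too small; if fading, too large), and changes specific to Group #2 at the switch are not removed.
5. For success, show both groups' proportions by period without an interaction test.

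The cost is a paragraph of text and a small added analysis, with no new patients, visits or data. The interval for the difference is about 1.4 times as wide (0.544 / 0.385), and one further assumption has to be defended. That is acceptable for an exploratory item, since the sample size was set for the primary endpoint.

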### 9.5 Per Protocol and Intent to Treat Analyses

Analyses of the primary and secondary effectiveness endpoints will be conducted on the intent-to-treat (ITT) population and the per-protocol (PP) population at each specified study interval defined as follows:

PP Population: The per-protocol population will consist of all randomized subjects who meet the following criteria:

- Were implanted [REDACTED]
- For Group #1 subjects: paresthesia coverage in the target areas.
- Have an adequate number of average pain intensity (BPI-5) scores in the diaries during the primary endpoint period (*i.e.*, first 4 weeks of home trial). These diaries must not be missing more than 50% of the pain scores to be included in the PP population.

[REDACTED]

- Continued study eligibility (subjects cannot have a change in medical status that would have otherwise excluded them from the study)

ITT Population: The intent-to-treat population will include all randomized patients who were implanted [REDACTED] that is, patients will be analyzed according to the treatment group to which they were randomized. Evaluable subjects are defined as those who were randomized and implanted with a lead.

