**7.5.2.9 Home Trial**

*At the end of Visit 2, subjects will be prepared to proceed to the home trial*

Group #1 subjects will be prepared to proceed to the home trial. The stimulation parameters will be set before the subject leaves the visit. [REDACTED]

Group #2 subjects will be prepared for the home trial. The site will ensure the Stimulator is placed in Sham mode before the subject leaves the visit. [REDACTED]

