The following variables: sex, age, baseline pain intensity, time elapsed from amputation, medications affecting pain used at baseline, prosthesis fit, baseline BDI-II score, and percent changes in usage of medication affecting pain between baseline and EOT (i.e., PRN medication usage) will be examined via a covariate analysis to determine their influence on the primary outcome.

**9.1.2 A power analysis of the 2-tailed, 2-sample Mann-Whitney test was conducted for the primary efficacy endpoint to determine the sample size for > 90% power and a 5% significance level**

A power analysis of the 2-tailed, 2-sample Mann-Whitney test was conducted with data from the previous feasibility study and data published in other studies. The proportion of successes expected for Group #1 was estimated from the previous feasibility study in which stimulation produced comfortable sensations (paresthesia) in the region of greatest pain. The proportion of successes expected for Group #2 was estimated from published studies in which sham (placebo) treatments were given to amputees with post-amputation pain. The null hypothesis that the proportion of successes of Group #1 is equal to the proportion of successes of Group #2 was tested.

[REDACTED]

[REDACTED]

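### In the visible text of 9.5 the per-protocol set drops Group #1 subjects without paresthesia coverage and has no counterpart for Group #2, so its comparison with sham is selected in one arm

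*Combined protocol and SAP*

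**What the plan says.** Section 9.5 states: "Analyses of the primary and secondary effectiveness endpoints will be conducted on the intent-to-treat (ITT) population and the per-protocol (PP) population". The visible PP criteria are implantation, no more than half of the pain scores missing in the first 4 weeks, continued eligibility and, for one arm, "For Group #1 subjects: paresthesia coverage in the target areas". No visible criterion does the same job for Group #2.

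The ITT set is the randomised subjects who were implanted, and "patients will be analyzed according to the treatment group to which they were randomized". The section adds: "Evaluable subjects are defined as those who were randomized and implanted with a lead". Neither statement carries a visible coverage filter.

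Two other places fix the timing. Section 7.5.3 shows that subjects who cannot be randomised never reach lead placement, so coverage becomes known only after randomisation. Section 7.5.2.9 says of Group #2: "The site will ensure the Stimulator is placed in Sham mode before the subject leaves the visit". Section 9.1 keeps that group on sham for the first 4 weeks, which is the primary endpoint period.

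Section 9.1 attributes any difference to stimulation because the arms are otherwise the same. If Group #1 is significantly better at p < 0.05, "it will indicate that the investigational treatment is clinically significant and different than the placebo effect". The visible rule does not say which population it applies to.

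**The concern.** Coverage is a response to active stimulation, seen after allocation and used to select in the active arm alone. On the PP set, a Group #1 cleared of subjects whom stimulation did not reach is compared with a Group #2 that keeps the subjects who would have been uncovered. The premise in 9.1 that the arms differ only in active versus sham stimulation no longer holds for that comparison. The secondary comparisons in 9.3 that set Group #1 against Group #2's sham period inherit the same selection when run on PP.

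Two things are at stake. First, the PP difference can be read as the effect in all implanted subjects when it is not. Second, if ITT misses p < 0.05 and PP meets it, the visible text does not say which result decides a study designed to demonstrate superiority (Synopsis, Study Design).

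**Working it through.** **Inputs from the documents.** 27 subjects per group (6.2); two-sided 5% level (9.1, 9.1.2); and, from 9.1.2, a power analysis "to determine the sample size for > 90% power and a 5% significance level". The expected success rates and the share of uncovered subjects are not visible.

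**The plan's own figure.** The stated power can be neither reproduced nor refuted without the success rates. With 27 per arm and a pooled two-proportion test, about 90% power corresponds to sham/active rates of 5/41%, 10/49%, 15/56%, 20/62%, 25/68% or 30/73%. The pair 15/56% (power 90.6%) is used below as one example.

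**Assumptions.** Uncovered share *f* = 10%, 20% or 30%; no other PP exclusions; uncorrected chi-square at 0.05, counting only wins for Group #1. Section 9.1.2 names Mann-Whitney; on a yes/no outcome its tie-corrected statistic is the chi-square times (N - 1)/N, so the two are nearly the same here. Win chances come from exact binomial enumeration, with ITT and PP evaluated on the same subjects.

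**Step 1: size of the difference if uncovered subjects succeed at the sham rate p2.** The rate in all implanted Group #1 subjects is p1 = (1 - f)·pc + f·p2, where pc is the rate in covered subjects. So pc - p2 = (p1 - p2)/(1 - f). The inflation is 1/0.9 = 1.11, 1/0.8 = 1.25 and 1/0.7 = 1.43. At 56% v 15% the 41-point difference becomes 45.6, 51.3 or 58.6 points.

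**Step 2: how often the two sets disagree when there is a real effect.** Each cell gives *f* = 10% / 20% / 30%.

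| Assumed rates | ITT win | PP win | PP wins alone |
|---|---|---|---|
| 56% v 15% in all implanted | 91.1% throughout | 94.3 / 97.2 / 99.0% | 3.3 / 6.1 / 7.8% |
| 56% in covered subjects only, 15% sham | 85.4 / 77.4 / 67.4% | 89.3 / 87.8 / 85.6% | 4.3 / 10.6 / 18.4% |

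The second row is plausible because 9.1.2 takes the Group #1 rate from a feasibility study in which stimulation did produce paresthesia in the region of greatest pain. ITT wins alone in under 1% of trials throughout, so disagreement runs almost entirely one way.

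**Step 3: false wins with no device effect, coverage unrelated to outcome.** For success rates of 15% to 40%, false Group #1 wins are 2.5-2.8% on PP and 2.3-2.9% on ITT. If a win on either set were accepted, the figure is 2.9-3.8%. There is no material inflation.

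**Step 4: false wins with no device effect, coverage related to prognosis.** Suppose subjects who can be covered succeed at 40% and the others at 10%, in both arms. At *f* = 20%, Group #2 succeeds at 0.8 × 40% + 0.2 × 10% = 34%. Filtered Group #1 succeeds at 40%, a spurious 6 points. False wins are 6.5% on PP against 2.6% on ITT. Over *f* = 10% to 30% the PP figure runs from 4.0% to 9.7%.

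**Step 5: sensitivity to single subjects.** A result of 12/27 v 6/27 gives Fisher p = 0.148. Removing three uncovered Group #1 failures gives 12/24 v 6/27, p = 0.046.

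**The case against.** The strongest reply is that this is an openly pre-stated PP set in a pilot, reported beside an ITT analysis without the filter. Selecting properly treated subjects is what a PP set does, and a larger PP difference may simply describe the effect where stimulation reached the painful area. That stands as far as description goes. It does not make a test of those subjects against unselected sham subjects a like-for-like comparison.

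Redaction also counts. Section 9.5 is blacked out within the PP list and within the ITT definition, 9.1 and its subsections have blacked-out parts, and neither 9.1.3 nor 7.5.2.2 to 7.5.2.5 is visible. A reader might infer that the plan has no Group #2 criterion, or that it never names the deciding population. The documents do not support either statement; only the visible text lacks them.

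A reader might also infer that the PP test has an inflated false-win rate. Step 3 shows this does not follow from the filter alone. It needs uncovered subjects to have a poorer prognosis whatever the stimulation, and nothing in the documents shows that. The opposite inference fails too. Section 9.1 says "Both groups are expected to experience a similar placebo effect from the study procedures and use of the devices", but that compares the two groups and says nothing about covered versus uncovered subjects.

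The PP set could even be the less distorted one. Suppose uncovered Group #1 subjects leave after Visit 2 (7.5.2.6) and count as failures through baseline imputation (9.1.5), with coverage unrelated to prognosis. At a 25% sham rate and no device effect, false wins are then 2.6-2.8% on PP and 0.5-1.7% on ITT, so ITT is conservative. Repeat lead placement for Group #1 non-responders (7.5.2.6) should also lower the uncovered share.

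Finally, implantation, diary completeness and continued eligibility are themselves observed after randomisation, so no PP set is strictly randomised. An outright ban on comparing covered subjects with sham would go further than needed.

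**Conclusion.** The point holds for the PP comparison on the visible text: a post-randomisation criterion is applied to Group #1 alone, and the set it produces is used for comparison with sham. If uncovered subjects succeed at the sham rate, the PP difference overstates the effect in all implanted subjects by 11% to 43% for 10% to 30% uncovered. False wins are not materially raised in that case; they are if uncovered subjects have a poorer prognosis, and the documents do not show which applies. All success rates and coverage shares here are assumptions.

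A reader might go further and conclude that the randomised comparison is lost. It is not: the ITT analysis has no visible coverage filter and is made by assigned group. What remains open in the visible text is which set decides if the two disagree. The weight lies between minor and should-fix.

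**What to change.** 1. In 9.1 and 9.5, state that the superiority conclusion at p < 0.05 rests on the ITT population analysed as randomised, and that PP is supportive. If redacted text already says so, confirming that is enough.
2. Remove the Group #1-only coverage criterion from the PP set used for the test against sham, and keep the criteria that apply to both arms. If a redacted passage holds a Group #2 counterpart, show that it is assessed in the same way in both arms. Results in covered Group #1 subjects may still be reported, labelled as a selected, non-randomised supportive comparison.

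The cost is wording only; no subject, visit or procedure changes. The PP estimate becomes less favourable: at the assumed 56% v 15% with 20% uncovered, the PP difference falls from about 51 to 41 points and the PP win chance from about 97% to 91%.

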**7.5.2.6 Home Trial or Subject Disposition**

*At the end of Visit 2, the subject will either:*

- 1) proceed to the home trial,*
- 2) return for another Visit 2, or*
- 3) be terminated from the study*

At the end of Visit 2, there are three options:

1. Proceed to home trial:

If all leads were placed, the subject will be prepared to proceed to the home trial.

2. Return for another Visit 2:

If there is not sufficient time to complete lead placement or the testing, or if the Group #1 subject does not respond to stimulation, the investigator may present the subject with the option to return for a repeat lead placement visit.

3. Terminate from the study:

If the subject does not wish to continue with further lead placement, they will be terminated from the study if no adverse events (AE) are noted at the 24-48 hour telephone follow-up. If an AE is noted the subject will be followed until the AE resolves.

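### The set called intent-to-treat is conditional on implantation after randomisation, no all-randomised analysis is visible, and the counting of Group #1 subjects who leave at Visit 2 is undefined

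*Combined protocol and SAP*

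**What the plan says.** Section 9.5 names two sets for the primary and secondary effectiveness endpoints.

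- **Intent-to-treat.** "The intent-to-treat population will include all randomized patients who were implanted", analysed by assigned group. The words directly after this are redacted. The section adds: "Evaluable subjects are defined as those who were randomized and implanted with a lead".
- **Per-protocol.** Randomised and implanted subjects who meet further conditions, one of which applies to one arm: "For Group #1 subjects: paresthesia coverage in the target areas".

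Randomisation (7.5.2.1) precedes lead placement. Section 7.5.3 confirms the order: people found ineligible for randomisation at Visit 2 get no follow-up call, because no lead was placed.

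Section 7.5.2.6 gives three outcomes at the end of Visit 2.

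- Subjects enter the home trial once all leads are placed; no response condition is stated.
- A repeat visit may be offered for lack of time ("If there is not sufficient time to complete lead placement or the testing"), in either group, or for non-response in one group: "if the Group #1 subject does not respond to stimulation, the investigator may present the subject with the option to return".
- Termination is worded for both groups: "If the subject does not wish to continue with further lead placement, they will be terminated from the study", subject to the adverse event check.

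A response check for Group #2 is visible only at Visit 7 (week 4), for subjects given replacement leads. Section 9.1 nevertheless says: "The groups will be identical except for whether active stimulation (Group #1) or sham stimulation (Group #2) is delivered during the first 4 weeks".

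**The concern.** Being implanted is a post-randomisation event. A set conditional on it keeps the benefit of randomisation only if the two arms lose the same kind of subject. Section 7.5.2.6 gives a reason to doubt that. In Group #1 a lack of response can lead to an offer of repeat placement, and refusing that offer ends participation. The visible text shows no response-based counterpart in Group #2 before the sham period ends.

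If Group #1 subjects who leave this way are not counted, likely failures disappear from one arm's denominator, and the Group #1 success rate rises without any treatment effect. Section 9.1 attributes a difference between the arms to the treatment on the ground that the groups are otherwise identical, so the loss would bear directly on the primary claim.

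The per-protocol set is no safeguard. It requires paresthesia coverage in Group #1 only, which is open selection on response in one arm. Agreement between the two sets would therefore not be reassuring.

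**Working it through.** **1. The plan's own figure.** Section 9.1.2 claims more than 90% power at a 5% significance level. The assumed success rates are redacted, so this cannot be reproduced. With 27 per arm (6.2), the uncorrected formula

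n = [1.96·√(2p̄(1−p̄)) + 1.2816·√(p₁(1−p₁)+p₂(1−p₂))]² / (p₁−p₂)²

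reaches 90% at, for example, 0.41 v 0.05, 0.62 v 0.20 or 0.73 v 0.30. Many control rates are compatible with the design, so a range is used below.

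**2. Who is in the set?** Two readings of 9.5 are open for a Group #1 subject whose lead is tested without response, who declines a repeat, and who is terminated.

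- *Counts as implanted with a lead.* The subject stays. If scored as a failure, the subject lowers the Group #1 rate.
- *Does not count,* because the lead was withdrawn or because of the redacted condition. The subject leaves the denominator.

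Section 9.1.5 does not settle this. It imputes the baseline mean for missing diary days in the first 4 weeks of the home trial. For a fully missing diary that gives 0% reduction, a failure. It does not clearly reach someone who never began the home trial.

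**3. Effect on the rate under the second reading.** Let p be the true success rate over 27 randomised per arm, and drop k Group #1 failures. The expected rate becomes about 27p/(27−k). At p = 0.20: 5.4/26 = 0.208 (k = 1), 5.4/24 = 0.225 (k = 3), 5.4/22 = 0.245 (k = 5).

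**4. Effect on false wins.** Inputs: 27 per arm (6.2); two-sided 0.05 (9.1, 9.1.2); a yes/no success per subject (9.1). The Mann-Whitney test is named in 9.1.2 for the power analysis; Fisher's exact test is added for comparison and is not named in the visible text. Assumed: p and k.

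S₁ and S₂ are independent Binomial(27, p). Group #1 is analysed as S₁ out of n₁ = 27−k (fewer dropped if there are fewer than k failures), Group #2 as S₂ out of 27. With N = n₁+27 and pooled proportion p̄, the tie-corrected Mann-Whitney statistic is

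z = (S₁/n₁ − S₂/27) / √[p̄(1−p̄)(1/n₁+1/27)·N/(N−1)].

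A false win is two-sided p < 0.05 with Group #1 higher. Exact enumeration gives, in %:

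| Test | k | p=0.10 | p=0.20 | p=0.30 | p=0.40 |
|---|---|---|---|---|---|
| Mann-Whitney | 0 | 2.56 | 2.38 | 2.50 | 2.31 |
| Mann-Whitney | 3 | 2.85 | 4.07 | 5.14 | 6.29 |
| Mann-Whitney | 5 | 5.68 | 6.57 | 9.03 | 10.94 |
| Fisher | 0 | 0.36 | 0.96 | 1.26 | 1.24 |
| Fisher | 3 | 2.58 | 2.91 | 3.81 | 4.63 |
| Fisher | 5 | 2.65 | 4.29 | 5.87 | 9.31 |

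The nominal one-sided level is 2.5%.

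**5. Exits unrelated to outcome.** With 24 v 27 and the same p in both arms over 10–40%, Mann-Whitney gives 1.9–2.7% and Fisher 1.7–2.0%. There is no inflation beyond the nominal level. Part of the Fisher rise in the table comes only from the unequal group sizes, which make that test less conservative.

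**6. One result at a time (illustrative counts).** Fisher: 12/27 v 5/27 gives p = 0.077; 12/26 v 5/27 gives 0.042; 12/24 v 5/27 gives 0.036. Other counts do not cross 0.05: 11/27 v 5/27 goes from 0.135 to 0.068 when three are dropped, and 13/27 v 5/27 is already 0.042. By Mann-Whitney, 12/27 v 5/27 is already 0.042. A changed verdict is possible, not typical.

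**The case against.** The strongest objection is that the two facts need not connect. A subject who does not respond to stimulation has normally had a lead placed, and the visible definition of an evaluable subject requires a lead, not a response or entry to the home trial. On that reading non-responders stay in the set, and scoring them as failures works against Group #1. This stands: bias toward the device is possible but not shown.

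A reader might also infer that Group #1 subjects alone can be ended for not responding. Section 7.5.2.6 does not say so. Termination follows the subject's own refusal of further placement, in either group; the repeat offer is at the investigator's discretion; and lack of time is a reason for a repeat in both arms. Only one reason for a repeat differs by arm.

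Nor can one say that Group #2 has no response check at Visit 2. Most of the text between randomisation and 7.5.2.6 is redacted, as are the early termination section and the text after the imputation rule. The visible text shows none; that is all.

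Section 6.2 gives the same ceiling, 54, for subjects randomised and subjects undergoing lead placement, so the plan seems to expect few losses. That bears on the likely size, but supplies no rule for those who do leave.

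What the objection does not remove is that the label is wrong on its face. The unredacted sentence on evaluable subjects repeats the implantation condition.

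**Conclusion.** The concern holds in a limited form. The set called intent-to-treat is a modified one, the visible text has no all-randomised analysis, and it leaves open how subjects who exit at Visit 2 are counted. The Group #1-only reason for repeat placement in 7.5.2.6 does not fit the statement in 9.1 that the groups differ only in stimulation.

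Whether the primary comparison is biased depends on the undefined point. If Group #1 non-responders who leave are excluded, it could favour Group #1. With 3 of 27 dropped, all failures, the false-win chance goes from about 2.3–2.6% to 2.9–6.3% (Mann-Whitney), or from 0.4–1.3% to 2.6–4.6% (Fisher), over null success rates of 10–40%. At the low end this is close to nominal. The success rates and number of exits are assumptions. A reader might conclude that the plan favours the device; the documents do not support that, because such subjects may well stay in the set. Confidence is moderate because of the redactions.

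**What to change.** - Define the primary intent-to-treat set as all randomised subjects in their assigned group.
- Count any subject with no home-trial diary (not implanted, or terminated at Visit 2) as a non-success, by the same rule in both arms.
- Define implanted, and say whether a lead that was tested and withdrawn qualifies.
- Keep the implanted set as a sensitivity analysis labelled modified intent-to-treat, and do not present the per-protocol set as confirmation.
- Report Visit 2 repeats, non-implantations and terminations by arm.
- Sections 7.5.2.6 and 9.1 must be reconciled.

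The cost is analysis wording and one disposition table; no change to sample size is needed. The downside is that the Group #1 success rate may look slightly lower, because exits in that arm would count against it.
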